5.6.4 Lipodystrophy/Fat Redistribution/Body Changes

Investigators should avoid using the term "lipodystrophy acquired" to describe and report fat redistribution abnormalities associated with ARV therapy as this term is not very descriptive. The different symptoms and gradings are listed in the DAIDS scale under 'Endocrine/Metabolic' (see Section 7.2, Addendum 2: DAIDS Grading Table). The relevant terms include: abnormal fat accumulation, lipoatrophy and gynecomastia.

Although metabolic abnormalities such as hyperlipidemia or hyperglycemia are often associated with body changes, these events should be reported separately for the purpose of AE reporting.

Assessment of fat redistribution in HIV-infected children and adolescents is complicated by the normal, dynamic alterations in body composition that occur during childhood and adolescence.

Children and adolescents can be considered to have abnormal fat accumulation if they have 1 or more of the following signs:

- Trunk with increased abdominal girth
- Dorso-cervix with fat accumulation 'buffalo hump'
- Breast enlargement

Children and adolescents can be considered to have lipoatrophy if they have 1 or more of the following signs:

- Face with sunken cheeks, sunken eyes with prominent zygomatic arch
- Skinny arms with prominent veins; muscularity and bones
- Skinny legs with prominent veins; muscularity and bones
- Buttocks with loose of skin folds, prominent muscles, loss of contour and fat

5.6.5 PANCREATITIS

Pancreatitis must be considered whenever a subject develops abdominal pain, nausea, vomiting, and/or elevated amylase or lipase. Temporary treatment interruption is allowed (including DRV/rtv and background regimen) in case of clinical suspicion and until the diagnosis of pancreatitis can be excluded.

It is not recommended to co-administer tenofovir disoproxil fumarate (TDF) and didanosine (ddI) in the OBR (if applicable) due to an increased risk of pancreatitis¹⁴.

5.6.5.1 Clinical Pancreatitis

Grade 1: not applicable.

Grade 2: symptomatic and hospitalization not indicated (other than emergency room visit).

Grade 3: symptomatic and hospitalization indicated (other than emergency room visit).

Grade 4: life-threatening consequences (e.g., circulatory failure, hemorrhage, sepsis).

5.6.5.2 Laboratory Abnormalities

For asymptomatic grade 1 and grade 2 pancreatic amylase and/or lipase elevations, and confirmed asymptomatic grade 3 pancreatic amylase elevations with no past or active history of pancreatitis, subjects should be carefully evaluated and followed closely.

For confirmed grade 4 elevations of pancreatic amylase and/or confirmed grade 3 or 4 elevations of lipase, subjects should interrupt therapy (including DRV/rtv and background regimen) until amylase returns to grade ≤ 2 , at which time therapy could be reintroduced. The NRTI(s) most likely related to the elevated lipase will be switched to another NRTI (see Section 5.3.5). If grade 4 elevations of pancreatic amylase and/or grade 3 or 4 lipase levels persist ≥ 14 days following interruption of therapy, or if the toxicity recurs more than twice, therapy (including DRV/rtv and background regimen) should be discontinued.

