5.2.5 REMOVAL OF SUBJECTS FROM THERAPY OR ASSESSMENT

A subject **may** be withdrawn from the trial if:

- 1. An SAE occurs.
- 2. The subject fails to comply with the protocol requirements or to cooperate with the investigator.
- 3. The subject starts disallowed treatment (see Section 5.3.12). The sponsor should be contacted to evaluate the need for withdrawal.
- 4. The subject demonstrates lack or loss of treatment response during the trial.

A subject **must** be withdrawn from the trial if:

- 1. The parent(s) or legal representative(s) withdraw(s) consent, or the subject withdraws consent or assent.
- 2. The investigator considers it, for safety reasons, in the best interest of the subject that he or she be withdrawn.
- 3. Pregnancy has been determined.
- 4. The subject is diagnosed with acute hepatitis A, B, or C infection after baseline. For details on monitoring and management of hepatitis, see Section 5.5.4.

- 5. The subject experiences a grade 3 or 4 cutaneous reaction/rash (according to the DAIDS scale; see Section 7.2, Addendum 2: DAIDS Grading Table). For details on monitoring and management of cutaneous reaction/rash, see Section 5.5.1.
- 6. The subject experiences a grade 4 AE considered at least possibly related to DRV/rtv or a confirmed grade 4 laboratory abnormality (according to the Division of AIDS [DAIDS] scale; see Section 7.2, Addendum 2: DAIDS Grading Table) considered at least possibly related to DRV/rtv. Exceptions are, unless clinical assessment foresees an immediate health risk to the subject:
- 7. Subjects with asymptomatic triglyceride grade 4 elevations (see Section 5.6.2). The subject experiences a persistent grade 3 or 4 glucose elevation despite appropriate anti-hyperglycemic treatment (except if the subject has pre-existing diabetes; see Section 5.6.1)
- 8. The subject experiences a confirmed grade 4 pancreatic amylase elevation or a confirmed grade 3 or grade 4 lipase elevation, which persists after 14 days after the interruption of the trial medication, or if the toxicity recurs more than twice (see also Section 5.6.5.2). The subject experiences, after trial medication interruption because of a confirmed grade 3 increase in alanine aminotransferase (ALT) or aspartate aminotransferase (AST), a confirmed recurrence of grade 3 or 4 increase in ALT or AST. For subjects with hepatitis B or C coinfection present at baseline, refer to Section 5.5.3 for toxicity management plans.

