5.5 Safety Monitoring and Toxicity Management

Toxicity management is at the discretion of the investigator, and is to take into account the protocol-defined procedures defined under 5.5.1, 5.5.2, 5.5.3, 5.5.4, 5.5.5, 5.5.6, 5.5.7, and 5.5.8, and the local standard clinical practice.

After termination of data collection, toxicity management will be performed per local standard of care and documented in the subject's medical records only.

The following guidelines are present in the Clinical Trial Protocols for ongoing HIV-1 trials of DRV. Participating investigators are strongly encouraged to follow these guidelines and to apply the same safety measures for subjects participating in this trial.

Note:For grade 3 or 4 laboratory toxicities, a confirmatory measurement within 48 hours after the laboratory results become available is mandatory. This management scheme is for confirmed laboratory abnormalities and not for isolated events.

The following laboratory abnormalities do not warrant mandatory confirmation within 48 hours:

- Subjects with asymptomatic triglyceride or cholesterol elevations of grade 3 or 4.

All adverse events occurring at any time during the trial will be followed until satisfactory clinical resolution (i.e., value back to baseline value) or stabilization or until final database lock. All grade 3 and grade 4 laboratory abnormalities and laboratory abnormalities resulting in an increase of 2 DAIDS grades from baseline will be followed until return to baseline or within 1 grade from baseline. Certain long-term adverse events of ARV therapy cannot be followed to resolution within the setting of this protocol; in these cases follow-up will be the responsibility of the treating physician, which will be agreed upon with the sponsor.

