5.5.8 OTHER TOXICITIES

Grade 1

Subjects who develop a grade 1 AE or toxicity may continue intake of the trial medication.

Grade 2

Subjects who develop a grade 2 AE or toxicity may continue intake of the trial medication based on the investigator's clinical judgment.

Note: For grade 3 or 4 laboratory toxicities, subjects should have a confirmatory measurement within 48 hours after the laboratory results become available. This management scheme is for confirmed laboratory abnormalities and not for isolated events.

Grade 3

Subjects who develop a grade 3 AE or toxicity should interrupt all medications (including DRV/rtv and OBR) and may resume all therapy when the AE or laboratory abnormality resolved to within one grade level (\leq grade 2) of the subject's baseline. The following exceptions apply:

- subjects who experience an asymptomatic glucose elevation of grade 3 (See Section 5.6.1);
- subjects who experience asymptomatic triglyceride or cholesterol elevations of grade 3 (See Section 5.6.2);
- subjects who experience asymptomatic pancreatic amylase elevations of grade 3 with no past or active history of pancreatitis (provided lipase is within normal limits) (See Section 5.6.5);
- subjects who experience an AE that is considered not related or doubtfully related to the study medication.

Grade 4

Subjects experiencing a grade 4 AE or toxicity will permanently discontinue medication (including DRV/rtv and OBR).

The following exceptions apply:

- subjects who experience asymptomatic triglycerides elevations of grade 4 (see also Section 5.2.5);
- subjects who experience an AE that is considered not related or doubtfully related to the trial medication.

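### Protocol 5.6.5.2 stops therapy for a confirmed grade 3 lipase rise but ties restart to amylase alone, so an isolated lipase rise meets the restart condition at once

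*Protocol*

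**What the plan says.** The interruption rule in Protocol 5.6.5.2 opens "For confirmed grade 4 elevations of pancreatic amylase and/or confirmed grade 3 or 4 elevations of lipase". Lipase alone is enough to trigger it. The instruction continues "subjects should interrupt therapy (including DRV/rtv and background regimen) until amylase returns to grade" 2 or below, and reintroduction is then permitted, not required. Lipase reappears in the next two sentences: "The NRTI(s) most likely related to the elevated lipase will be switched to another NRTI", and therapy is to be discontinued "If grade 4 elevations of pancreatic amylase and/or grade 3 or 4 lipase levels persist" for 14 days or more after interruption, or if the toxicity recurs more than twice. Section 5.2.5, criterion 8, repeats the stopping rule as a reason for withdrawal: "or a confirmed grade 3 or grade 4 lipase elevation, which persists after 14 days after the interruption of the trial medication".

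The general grade 3 rule in 5.5.8 is framed differently. Subjects interrupt and "may resume all therapy when the AE or laboratory abnormality resolved to within one grade level", glossed there as grade 2 or below. Its listed exceptions include asymptomatic grade 3 amylase with no history of pancreatitis, provided lipase is normal, but not grade 3 lipase. They also include "subjects who experience an AE that is considered not related or doubtfully related to the study medication".

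**The concern.** A restart rule should depend on the abnormality that caused the stop. Here lipase can cause the stop, but only amylase governs the restart. Read literally, a subject with an isolated grade 3 lipase rise is told to interrupt and may restart the same day, with the lipase rise unresolved.

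At stake is re-exposure to DRV/rtv and a background regimen while a marker of pancreatic injury is still at grade 3. Early restart also weakens the 14-day stopping rule, because persistence is then no longer judged off drug, and recurrences are hard to count if the first episode never resolved.

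Section 5.4.4.2 adds a smaller difficulty: routine biochemistry may include amylase, if available, or lipase. Where only lipase is measured, the restart condition cannot be assessed. The documents do not say whether any site works this way.

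**Working it through.** There is no stated figure to reproduce. The check applies the written rule to the grading limits.

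**Inputs** (Protocol Addendum 2, in multiples of ULN):

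| Grade | Lipase | Pancreatic amylase |
|---|---|---|
| 1 | 1.1 to 1.5 | 1.1 to 1.5 |
| 2 | > 1.5 to 3.0 | > 1.5 to 2.0 |
| 3 | > 3.0 to 5.0 | > 2.0 to 5.0 |
| 4 | > 5.0 | > 5.0 |

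**Rules**

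- Interrupt (5.6.5.2): confirmed amylase grade 4, or confirmed lipase grade 3 or 4.
- Restart as written (5.6.5.2): amylase at grade 2 or below.
- Restart as proposed: the triggering enzyme at grade 2 or below, and both if both were raised.

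**Confirmed grade 3 lipase at each possible amylase level**

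| Amylase at interruption | Interruption triggered | Written restart test already met | Proposed restart test already met |
|---|---|---|---|
| Normal | yes | yes | no |
| Grade 1 | yes | yes | no |
| Grade 2 | yes | yes | no |
| Grade 3 | yes | no | no |
| Grade 4 | yes | no | no |
| Total | 5 of 5 | 3 of 5 | 0 of 5 |

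In the last two rows the written test waits for amylase to fall but still ignores lipase.

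**Example.** Confirmed lipase is 4.0 x ULN (grade 3) and amylase is 1.4 x ULN (grade 1).

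- Under 5.6.5.2, therapy is interrupted and the restart test is true the same day.
- Under 5.5.8, if the rise is at least possibly related, lipase must first fall to 3.0 x ULN or less.
- Under 5.5.8, if the rise is reported as an AE judged not or doubtfully related, no interruption is required, so that section offers no stricter restart rule.

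**Duration.** If the 14-day clock in 5.6.5.2 starts at interruption, the gap runs from day 0 to day 13, since persistence to day 14 triggers discontinuation. Section 5.2.5 words the limit as persistence after 14 days, so the endpoint differs slightly between the two sections.

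**Other sections.** Section 5.6.5 requires pancreatitis to be considered when either enzyme is raised. Section 5.5 adds "All grade 3 and grade 4 laboratory abnormalities and laboratory abnormalities resulting in an increase of 2 DAIDS grades from baseline will be followed". Neither gives a lipase level for restart, and neither does the NRTI switch. The 14-day rules say when to stop for good, not when to resume.

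**The case against.** The strongest reply is that the text should not be read so literally. The word *returns* presupposes that amylase was raised, and the rest of the paragraph plainly treats lipase as something to act on and track. On this view a word is missing and no investigator would restart the same day. That is probably how it arose, but a missing word in an operative rule still leaves the rule wrong.

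The second reply is that 5.5.8 supplies the threshold. It does not exempt grade 3 lipase, its exceptions cross-refer to 5.6.5, and the two rules can be met together because restart under 5.6.5.2 is only permitted. This has force for rises at least possibly related to treatment. However, the two sections then give different conditions for the same event, and 5.6.5.2 neither repeats nor cites 5.5.8. If the specific section is taken to override the general one, no lipase restart threshold remains.

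The third reply concerns weight, and it stands. Section 5.6 leaves toxicity management to the investigator, taking the protocol procedures into account. Restart follows a switch of the suspected NRTI. Under Amendment 2 the next planned visit is the Final/Withdrawal Visit, after which management follows local standard of care, so the clause has a short remaining life for each subject. The 3 of 5 count says nothing about how often the situation occurs. The lipase-only difficulty is hypothetical and does not itself argue for premature restart. These points limit the severity; they do not correct the clause.

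**Conclusion.** The concern holds, at minor severity. As written, 5.6.5.2 allows therapy to resume with lipase still above 3.0 and up to 5.0 x ULN whenever amylase is 2.0 x ULN or less, and that condition is already satisfied at interruption for an isolated grade 3 lipase rise.

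This rests on the plain wording of the section and the Addendum 2 limits. The day 0 to 13 window assumes that the clock runs from interruption. The documents give no joint amylase and lipase data, so frequency is unknown. The conflict with 5.5.8 is confined to grade 3 rises considered at least possibly related. No claim is made about grade 4 lipase.

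No analysis is affected: SAP section 1.2 states that safety laboratory results were assessed locally and not transferred to the database for formal analysis.

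**What to change.** In Protocol 5.6.5.2, replace the amylase-only restart condition with this: therapy may be reintroduced once whichever of pancreatic amylase and lipase triggered the interruption has returned to grade 2 or below, and both have done so if both were raised. Taking *raised* to mean above grade 2 keeps the existing amylase condition and loosens nothing. It also gives a usable rule where only lipase is measured, and it matches the other interrupt-and-resume rules (AST/ALT, nausea, diarrhea and 5.5.8), which depend on the toxicity that caused the stop.

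An optional harmonisation, not a separate error, is to carry the 5.5.8 requirement of normal lipase into the 5.6.5.2 sentence on asymptomatic grade 3 amylase.

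The cost is a one-line clarification. No new assessment is needed, because the triggering enzyme has already been measured and confirmed, and 5.5 already requires it to be followed. If the change were classed as substantial, ethics committee approval would be needed before implementation (Part II, section 6.2).

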5.6.6 Hypersensitivity Reactions

In clinical studies approximately 5% of subjects receiving an ABC-containing product developed a hypersensitivity reaction, which in rare cases has been proven fatal¹¹.

At baseline, it is recommended to test subjects without prior documented HLA-B*5701 negative results in whom the investigator considers ABC/3TC as background regimen to avoid hypersensitivity reactions. In those subjects where HLA-B*5701 is tested positive, ABC should not be administered¹². In this case, the investigator must select another background regimen (without ABC) consisting of at least 2 NRTIs (see Section 5.3.5 for more details about the background regimen).

It should also be noted that HLA screening and exclusion of HLA-B*5701 positive subjects does not completely eliminate the risk of hypersensitivity reactions.

5.6.6.1 Description of the Hypersensitivity Reaction

The ABC hypersensitivity reaction is characterized by the appearance of symptoms indicating multi-organ involvement. The majority of subjects have fever and/or rash as part of the syndrome, however reactions have occurred without rash or fever.

Other signs and symptoms may include respiratory signs and symptoms such as dyspnea, sore throat, cough and abnormal chest x-ray findings (predominantly infiltrates, which can be localized), gastrointestinal symptoms, such as nausea, vomiting, diarrhea, or abdominal pain, and may lead to misdiagnosis of hypersensitivity as respiratory disease (pneumonia, bronchitis, pharyngitis), or gastroenteritis. Other frequently observed signs or symptoms of the hypersensitivity reaction may include lethargy or malaise and musculoskeletal symptoms (myalgia, rarely myolysis, arthralgia).

The symptoms related to this hypersensitivity reaction worsen with continued therapy and can be life-threatening. These symptoms usually resolve upon discontinuation of ABC.

5.6.6.2 Management of Hypersensitivity Reactions

Subjects developing signs or symptoms of hypersensitivity must contact their doctor immediately for advice.

If a hypersensitivity reaction is diagnosed, the subject must discontinue ABC treatment immediately. The background regimen will be replaced by an alternative background regimen (see Section 5.3.5).

The subject should be asked to return all unused supplies of the ABC-containing product for disposal to prevent an accidental re-challenge.

An ABC-containing medicinal product (Ziagen®, Trizivir®, or Epzicom®/Kivexa®) must never be administered following a hypersensitivity reaction, as more severe symptoms will recur within hours and may include life-threatening hypotension and death.

To avoid a delay in diagnosis and minimize the risk of a life-threatening hypersensitivity reaction, the ABC-containing product should be permanently discontinued if hypersensitivity cannot be ruled out, even when other diagnoses are possible (respiratory diseases, flu-like illness, gastroenteritis, or reactions to other medications).

Symptomatic support for ABC hypersensitivity may be indicated. This should include, for example, administration of intravenous fluids to subjects who develop hypotension. Antihistamines or corticosteroids have been used in cases of ABC hypersensitivity, however, there are no clinical data demonstrating the benefit of these in the management of the reaction.

Laboratory and other investigations which may be useful in the evaluation and treatment of ABC hypersensitivity include, but may not be limited to, measurement of ALT, AST, creatine phosphokinase, serum creatinine, and WBC differential count and chest x-ray, if respiratory symptoms are present.

5.6.6.3 Special Considerations Following an Interruption of ABC Therapy

If therapy with ABC has been discontinued and restarting therapy is under consideration, the reason for discontinuation should be evaluated to ensure that the subject did not have symptoms of a hypersensitivity reaction. If a hypersensitivity reaction cannot be ruled out, no medicinal product containing ABC should be restarted.

There have been infrequent reports of hypersensitivity reaction following reintroduction of an ABC-containing product where the interruption was preceded by a single key symptom of hypersensitivity (rash, fever, malaise/fatigue, gastrointestinal symptoms, or a respiratory symptom). If a decision is made to restart any ABC-containing product in these subjects, this should be done only under direct medical supervision.

On very rare occasions hypersensitivity reactions have been reported in subjects who have restarted therapy, and who had no preceding symptoms of a hypersensitivity reaction. If a decision is made to restart an ABC-containing product, this must be done only if the subject or others can access medical care readily.

5.6.6.4 Essential Subject Information

An Alert Card is available in the commercial medication pack containing ABC to remind the subject and the medical staff about ABC hypersensitivity. This card should be removed and kept with the subject at all times.

Investigators must ensure that subjects are fully informed regarding the following information on the hypersensitivity reaction:

- Subjects must be made aware of the possibility of a hypersensitivity reaction to ABC that may result in a life-threatening reaction or death.
- All subjects without prior documented HLA-B*5701 negative results in whom the investigator considers ABC/3TC as background regimen should be tested for HLA-B*5701 (refer to ABC prescribing information/package inserts). In those subjects where HLA-B*5701 is tested positive, ABC should not be administered¹².
- Subjects developing signs or symptoms possibly linked with a hypersensitivity reaction must contact their doctor immediately.
- Subjects who are hypersensitive to ABC should be reminded that they must never take any ABC-containing medicinal product (Ziagen[®], Trizivir[®], or Epzicom[®]/Kivexa[®]) again.
- In order to avoid restarting the ABC-containing product, subjects who have experienced a hypersensitivity reaction should be asked to return the remaining tablets to the site.
- Subjects who have stopped taking an ABC-containing product for any reason, and particularly due to possible adverse events or illness, must be advised to contact their doctor before restarting.

5.6.6.5 Reporting of Hypersensitivity Reaction

All cases of potential ABC hypersensitivity should be reported as a serious adverse event (see Part II, Section 1.4 'Reporting of Adverse Events and HIV-Related Events').

5.7 Statistical Methods Planned and Determination of the Sample Size

5.7.1 SAMPLE SIZE CALCULATION

Since the objective of the trial is only to provide continued access to DRV/rtv for HIV-1 infected adult or pediatric subjects who previously received DRV/rtv in a clinical (parent) trial, who continue to benefit from using it, and who live in a country where DRV is not commercially available for the subject, is not reimbursed, or is not accessible through another source (e.g., access program, government program), and since the trial is not set up to show a specific statistical hypothesis, a sample size calculation is not applicable.

Data from this trial may be included in safety updates.

